### 3. Introduction

MK-7162 is a selective small-molecule inhibitor of Indoleamine-2,3-dioxygenase-1 (IDO1), administered orally, in development for use in combination therapy with pembrolizumab for the treatment of advanced solid tumors.

#### 3.1 Study Rationale

The IDO1 protein contains a heme co-factor which is responsible for binding and activating oxygen to catalyze the ring opening of L-tryptophan (TRP) to generate N-formyl kynurenone (KYN). The presence of heme is indispensable for IDO1 catalytic activity. MK-7162 inhibits IDO1 by either displacing heme from intact protein and/or preventing binding of heme during protein synthesis and folding. In human cancers, the enzyme IDO1 is upregulated and facilitates evasion of the immune system by tumor cells. MK-7162 is a small molecule which inhibits activity of IDO1, thereby reducing conversion of TRP to KYN, and facilitating T-cell responses within the tumor microenvironment.

While there is no prior experience with dosing of MK-7162 in humans with cancer, clinical proof of concept for IDO1 inhibition in cancer is provided by epacadostat, an IDO1-selective heme-binding inhibitor, that has been used clinically in combination with both anti-programmed death 1 (PD-1) antibodies, including pembrolizumab [Gangadhar TC, Hamid O, Smith DC, Bauer, TM, Wasser, JS, Luke JJ 2015], and anti-CTLA4 antibody ipilimumab [Gibney GT, Hamid O, Lutzky, J, Olszanski, AJ, Gangadhar, TC 2015]. To date, epacadostat has demonstrated a favorable safety profile in humans.

Initiation of human studies of MK-7162 is supported by preclinical studies conducted in rats and dogs. Based on the dosing margins established in preclinical safety studies of MK-7162, there are no contraindications to conducting clinical trials in accordance with study protocols and applicable regulatory guidance. To date, the safety of single doses of MK-7162 up to 300 mg has been established in an ongoing normal human volunteer (NHV) single ascending dose (SAD) study.

IDO1 expression is highly correlated with programmed death ligand 1 (PD-L1) expression in human tumors. IDO1 expression is induced in preclinical models in response to anti- PD-1 treatment as well as treatment with other immunomodulatory agents. Therefore, MK-7162 will be developed for use in combination with pembrolizumab, an anti-PD-1 agent.

#### 3.2 Background

Refer to the Investigator's Brochure (IB) for detailed background information on MK-7162, and the MK-3475 IB/approved labeling for detailed background information on pembrolizumab.

##### 3.2.1 Pharmaceutical and Therapeutic Background

###### 3.2.1.1 MK-7162 Pharmaceutical and Therapeutic Background

Malignant cells are known to evade the human immune system through a process known as immune tolerance. In recent years, immunotherapeutics have been developed that successfully counteract various cellular processes involved in cancer immune tolerance. Such therapies have expanded the range of options for treatment of various cancers. For example,

pembrolizumab is a monoclonal antibody that blocks the activity of PD-1, an immune checkpoint protein that promotes immune tolerance by suppressing T-cell activity against tumor cells. By blocking this pathway, pembrolizumab enables the antitumor immune response and has been shown to be efficacious in treatment of multiple malignancies including non-small cell lung cancer (NSCLC), malignant melanoma, head and neck squamous cell cancer (HNSCC), and Hodgkin lymphoma. However, despite the advances made in cancer immunotherapy, response to pembrolizumab treatment as well as to other immunotherapies is incomplete in many cases, and evidence suggests that malignant cells are able to utilize multiple other pathways to achieve immune escape.

IDO1 is an intracellular enzyme that catalyzes the first step of degradation of the essential amino acid TRP into KYN. Depletion of TRP and accumulation of KYN appear to interfere with multiple pathways required for T-cell activation and function. Studies demonstrate that expression of IDO1 by tumor cells in animal models leads to suppression of T-cell responses to tumor cells, contributing to immune tolerance.

MK-7162 is a selective small-molecule inhibitor of IDO1 that displaces the heme cofactor of IDO1, either by replacement of heme in the intact protein or by binding in place of heme during protein synthesis/folding. In vitro, MK-7162 shows potent inhibition of IDO1 in human cancer cells. Although MK-7162 is not directly cytotoxic to malignant cells, it is anticipated that inhibition of IDO1 activity will interfere with the immune tolerance phenomenon and enhance the antitumor effects of immunotherapeutic agents such as pembrolizumab.

MK-7162 NHV single ascending-dose study yielded the following safety data. There were no serious adverse events (SAEs) reported. The reported AEs were low grade. Epacadostat is a small-molecule inhibitor of IDO1 which is currently being studied in clinical cancer trials in combination with PD-1 blockade. While the mechanism of IDO1 inhibition by this compound is distinct from that of MK-7162, the common molecular target supports the projected effects common to both.

Epacadostat Phase 1/2 data demonstrated the following: one DLT occurred at the dose of 300 mg BID (grade 3, radiation pneumonitis); another DLT occurred at 400 mg BID (grade 3, fatigue). The most common adverse events in >20% of patients overall were fatigue, nausea, decreased appetite, vomiting, constipation, abdominal pain, diarrhea, dyspnea, back pain, and cough. Treatment produced significant dose-dependent reductions in plasma KYN levels and in the plasma KYN:TRP ratio at all doses and in all patients. Epacadostat doses of 100 mg BID achieved >80% to 90% inhibition of IDO1 at peak and 50% inhibition at trough based on plasma KYN:TRP ratios. Although no objective responses were detected, stable disease lasting greater than or equal to 16 weeks was observed in 7 of 52 patients [Beatty, G. L., et al 2017]. Grade 3 AST/ALT elevation was observed in 1 patient but was attributed to biliary duct obstruction consistent with progressive disease. A second patient also experienced grade 3 AST/ALT elevations, but this was determined to be most likely related to acetaminophen ingestion over the maximum recommended daily dose for tumor fevers.

BMS-986205, an IDO1 inhibitor with similar mechanism of action to that of MK-7162, is being evaluated in an ongoing clinical study in combination with the anti-PD-1 mAb nivolumab. Forty-two treated patients were reported. All treatment-related adverse events were grade 1 or 2 except three grade 3 toxicities (autoimmune hepatitis [dose limiting; BMS-986205 100 mg/nivolumab 240 mg], rash, and asymptomatic hypophosphatemia). Day 14 individual trough concentrations began exceeding the human whole blood 50% maximal inhibitor concentration ( $IC_{50}$ ) starting with 25 mg QD, and the 90% maximal inhibitor concentration ( $IC_{90}$ ) starting with 50 mg QD. All patients treated at 200 mg QD exceeded the  $IC_{90}$ . Serum KYN was substantially reduced at all doses (>45% mean reduction at each dose), with >60% mean reduction at the 100 and 200 mg QD doses. Intratumoral KYN was reduced from between 23% and 90% in evaluable paired pre- and monotherapy on-treatment samples [Siu, L. L., et al 2017] [Hunt, J. T., et al 2017].

### 3.2.1.2 Pembrolizumab (MK-3475) Pharmaceutical and Therapeutic Background

The importance of intact immune surveillance function in controlling outgrowth of neoplastic transformations has been known for decades [Disis, M. L. 2010]. Accumulating evidence shows a correlation between tumor-infiltrating lymphocytes in cancer tissue and favorable prognosis in various malignancies. In particular, the presence of CD8+ T-cells and the ratio of CD8+ effector T cells/FoxP3+ regulatory T-cells (T-reg) correlates with improved prognosis and long-term survival in solid malignancies, such as ovarian, colorectal, and pancreatic cancer; hepatocellular carcinoma; malignant melanoma; and renal cell carcinoma. Tumor-infiltrating lymphocytes can be expanded ex vivo and reinfused, inducing durable objective tumor responses in cancers such as melanoma [Dudley, M. E., et al 2005] [Hunder, N. N., et al 2008].

The PD-1 receptor-ligand interaction is a major pathway hijacked by tumors to suppress immune control. The normal function of PD-1, expressed on the cell surface of activated T cells under healthy conditions, is to down-modulate unwanted or excessive immune responses, including autoimmune reactions. PD-1 (encoded by the gene *Pdcd1*) is an immunoglobulin (Ig) superfamily member related to cluster of differentiation 28 (CD28) and cytotoxic T-lymphocyte-associated protein 4 (CTLA-4) that has been shown to negatively regulate antigen receptor signaling upon engagement of its ligands (PD L1 and/or PD-L2) [Greenwald, R. J., et al 2005] [Okazaki, T., et al 2001].

The structure of murine PD-1 has been resolved [Zhang, X., et al 2004]. PD-1 and its family members are type I transmembrane glycoproteins containing an Ig-variable-type (IgV type) domain responsible for ligand binding and a cytoplasmic tail responsible for the binding of signaling molecules. The cytoplasmic tail of PD-1 contains 2 tyrosine-based signaling motifs, an immunoreceptor tyrosine-based inhibition motif, and an immunoreceptor tyrosine-based switch motif. Following T-cell stimulation, PD-1 recruits the tyrosine phosphatases, SHP-1 and SHP-2, to the immunoreceptor tyrosine-based switch motif within its cytoplasmic tail, leading to the dephosphorylation of effector molecules such as CD3 zeta (CD3 $\zeta$ ), protein kinase C-theta (PKC $\theta$ ), and zeta-chain-associated protein kinase (ZAP70), which are involved in the CD3 T-cell signaling cascade [Okazaki, T., et al 2001] [Chemnitz, J. M., et al 2004] [Sheppard, K-A, et al 2004] [Riley, J. L. 2009]. The mechanism by which PD-1 down-modulates T cell responses is similar to, but distinct from, that of CTLA-4, because both molecules regulate an overlapping set of signaling proteins [Parry, R. V., et al 2005].

[Francisco, L. M., et al 2010]. As a consequence, the PD-1/PD-L1 pathway is an attractive target for therapeutic intervention in solid tumors.

Pembrolizumab is a potent humanized immunoglobulin G4 (IgG4) monoclonal antibody (mAb) with high specificity of binding to PD-1, thus inhibiting its interaction with programmed cell death ligand 1 (PD-L1) and programmed cell death ligand 2 (PD-L2). Based on preclinical in vitro data, pembrolizumab has high affinity and potent receptor blocking activity for PD-1. Pembrolizumab has an acceptable preclinical safety profile and is in clinical development as an intravenous (IV) immunotherapy for advanced malignancies. Keytruda™ (pembrolizumab) is indicated for the treatment of patients across a number of indications. Refer to the pembrolizumab IB/approved labeling for details.

### **3.2.2 Preclinical Trials**

#### **3.2.2.1 MK-7162 Preclinical Trials**

Refer to the MK-7162 IB for detailed preclinical information.

### **3.2.3 Ongoing Clinical Trials**

#### **3.2.3.1 MK-7162 Ongoing Clinical Trials**

A NHV trial for MK-7162 is ongoing. Refer to the MK-7162 IB for clinical trial details.

#### **3.2.3.2 Pembrolizumab (MK-3475) Ongoing Clinical Trials**

Ongoing clinical trials with pembrolizumab are being conducted in multiple solid tumors. In addition, multiple other agents in combination with pembrolizumab are also being investigated. Refer to the pembrolizumab IB for clinical trial details.

### **3.3 Benefit/Risk Assessment**

Participants in clinical trials generally cannot expect to receive direct benefit from treatment during participation, as clinical trials are designed to provide information about the safety and effectiveness of an investigational medicine.

Additional details regarding specific benefits and risks for participants participating in this clinical trial may be found in the accompanying IB and Informed Consent documents.

#### 4. Objectives/Hypotheses and Endpoints

In male and female participants at least 18 years of age with advanced solid tumors:

Objective	Endpoint
Primary	
1. To determine the safety and tolerability and to establish a preliminary RP2D of MK-7162 administered in combination with pembrolizumab	

• Dose-limiting toxicity (DLT)

• Adverse events (AEs)

• Discontinuation of study treatment due to an AE

Secondary	
1. To evaluate the pharmacokinetics (PK) of MK-7162 administered orally as monotherapy and in combination with pembrolizumab intravenous (IV) infusion	

• PK parameters of MK-7162, including area under the curve (AUC), <math>C_{\min}</math>, and <math>C_{\max}</math>

2. To evaluate pharmacodynamics (PD) of MK-7162 through measurement of KYN and TRP levels	

• KYN and TRP will be measured as PD markers of IDO1 inhibition.

3. To evaluate the objective response rate (ORR) of MK-7162 in combination with pembrolizumab	

• ORR based on Response Evaluation Criteria In Solid Tumors version 1.1 (RECIST 1.1) and immune-based RECIST (iRECIST) as assessed by the Investigator

Tertiary/Exploratory	
1. To evaluate overall survival (OS) and Progression Free Survival (PFS) of participants treated with MK-7162 in combination with pembrolizumab	

• OS

• PFS based on Response Evaluation Criteria in Solid Tumors version 1.1 (RECIST 1.1) and immune-based RECIST (iRECIST) as assessed by the Investigator

2. To evaluate the PK of pembrolizumab when administered in combination with orally administered MK-7162	

• PK parameters of pembrolizumab, including area under the curve (AUC), <math>C_{\min}</math>, and <math>C_{\max}</math>

3. To identify molecular (genomic, metabolic and/or proteomic) biomarkers that may be indicative of clinical response/resistance, safety, PD activity, and/or the mechanism of action of MK-7162 as monotherapy and in combination with pembrolizumab	

• Molecular (genomic, metabolic, and/or proteomic) determinants of response or resistance to treatments, using blood and/or tumor tissue; pembrolizumab anti-drug antibodies (ADA).

## **5. Study Design**

### **5.1 Overall Design**

This is a nonrandomized, multicenter open-label trial of MK-7162 in combination with pembrolizumab in participants with a histologically or cytologically confirmed diagnosis of advanced solid tumor.

Part A, the Dose Escalation and Confirmation Phase as outlined in this protocol, will follow the mTPI method (see Section 5.5.3.1) to identify a RP2D, MTD and/or MAD of MK-7162 for use in combination with pembrolizumab.

Upon identification of the preliminary RP2D of MK-7162 for use in combination with pembrolizumab, an amendment will be issued to this protocol. That amendment will contain the study details of Part B, the Dose Expansion Phase for participants with specified solid tumor types to receive MK-7162 in combination with pembrolizumab either as dual therapy or plus an additional chemotherapeutic or immune-modulatory agents.

#### **5.1.1 Dose Escalation and Confirmation**

This study will evaluate the safety and tolerability of MK-7162 alone and the safety, tolerability, and preliminary efficacy of MK-7162 in combination therapy with pembrolizumab.

All participants will be required to undergo a newly performed tumor biopsy during Screening, unless deemed medically unsafe by the Investigator. An additional on-study biopsy at one of two timepoints will also be required, unless deemed medically unsafe by the Investigator, with the biopsy at the other time point being optional. Initially, this biopsy will be required to occur on Cycle 2 Day 1 predose (prior to administration of MK-7162 study medication and prior to administration of IV pembrolizumab on that day), with a Cycle 3 Day 15 biopsy being optional. This will allow full characterization of the MK-7162 dose and intratumoral PD response relationship after three weeks of MK-7162 monotherapy. In addition, this tissue biopsy will facilitate characterization of the MK-7162 dose that maximally inhibits intratumoral IDO1. After a sufficient number of biopsy specimens at the Cycle 2 Day 1 timepoint have been collected, the Sponsor may notify the sites that the Cycle 2 Day 1 biopsy will become optional and the Cycle 3 Day 15 biopsy will be required. Characterization of the MK-7162 dose and intratumoral PD response relationship at this time point will confirm whether the intratumoral PD effect of a given MK-7162 dose is maintained during concurrent PD-1 blockade with pembrolizumab, since IDO1 upregulation occurs during immune responses.

Treatment allocation will be accomplished by nonrandom assignment through the interactive voice response system/integrated web response system IVRS/IWRS. Participants will receive MK-7162 monotherapy during the first treatment cycle followed by MK-7162 in combination with pembrolizumab for subsequent cycles.

MK-7162 will be administered PO QD, every day of each 21-day (3-week) cycle. Starting on Cycle 2, Day 1, MK-7162 will be administered in combination with pembrolizumab 200 mg IV, which will be administered on Day 1 of every cycle (every 3 weeks). The DLT evaluation period will be 2 cycles (6 weeks). Treatment of the first and second participants

enrolled in each cohort will occur at least 7 days apart. Treatment of the second and third participants enrolled in each cohort will occur at least 3 days apart.

An mTPI design [Ji, Y. and Wang, S.-J. 2013] will be used to identify and confirm the RP2D of MK-7162 in combination with pembrolizumab. Participants will initially be enrolled in the first dose-level cohort, receiving MK-7162 monotherapy for Cycle 1, and then receiving MK-7162 in combination with pembrolizumab for subsequent cycles (Cycles 2 to Cycle 36). Lower and/or higher doses of MK-7162 may then be explored depending on the combined safety, PK, PD, and preliminary efficacy data available at each dose level. The dose of pembrolizumab will remain constant at 200 mg IV Q3W.

The final number of participants enrolled will depend on the DLT observations and what dose is ultimately identified as the RP2D using the mTPI design. For the purposes of dose escalation decisions from a safety perspective, participants will be considered evaluable for DLT if they have completed the 6-week DLT evaluation period (completed the first and second cycles or discontinued treatment due to a DLT).

Dose finding and confirmation in Part A of the trial will end after 14 participants have been treated at any of the selected doses (which may include optional doses). In the event the dose-finding decision is not to stay at the current dose based on the 14 participants, the dose may be escalated or de-escalated and additional participants may be treated. The pool-adjacent-violators algorithm [Ji, Y. and Wang, S.-J. 2013] will be used to estimate the DLT rates under the assumption of monotonicity between DLT rates and dose levels. The dose with an estimated DLT rate closest to 30% may be treated as a preliminary RP2D. The totality of the data will be considered before deciding on the dose(s) to carry forward to Part B (dose expansion).

The primary objective is to identify the RP2D of MK-7162 for use in combination with pembrolizumab. The preliminary RP2D may be the same as the MTD/MAD, or the preliminary RP2D may be selected based on overall exposure, emerging safety and tolerability data, PK data, PD data, and preliminary clinical benefit data from this study.

Upon identification of the preliminary RP2D of MK-7162 for use in combination with pembrolizumab, additional participants with solid tumors will be enrolled in the dose expansion phase (Part B) of this trial to receive MK-7162 in combination with pembrolizumab as dual therapy, or in combination with additional chemotherapeutic or immune-modulatory agents. This dose expansion phase (Part B) of this trial will be initiated through a future protocol amendment.

Preliminary efficacy will be evaluated using objective response rate (ORR) and Progression Free Survival (PFS) assessed by the investigator based on the RECIST 1.1. ORR and PFS will also be assessed by iRECIST. ORR will be evaluated as a secondary objective. PFS and overall survival (OS) will be evaluated as exploratory objectives.

Participants will be monitored carefully for the development of AEs, and for clinical and/or radiographic evidence of disease progression according to RECIST 1.1. However, iRECIST may be used by the investigator for treatment decision. In participants who have initial evidence of radiological progressive disease by RECIST 1.1, it will be at the discretion of the investigator whether to continue a participant on study treatment until repeat imaging is obtained. This clinical judgment decision should be based on the participant's overall clinical

condition, including performance status, clinical symptoms, and laboratory data. Participants may continue to receive study treatment until tumor assessment is repeated  $\geq 4$  weeks later and confirms progressive disease by iRECIST per site assessment.

Adverse events will be evaluated by the investigator, according to criteria outlined in the National Cancer Institute (NCI) Common Toxicity Criteria for Adverse Events (CTCAE), version 4.0, to establish the safety and tolerability of MK-7162 when administered as monotherapy and in combination with pembrolizumab, as per the primary objective of this study.

There will be no intra-participant dose escalation for participants enrolled in this study. The definition of DLTs and criteria for dose modification of MK-7162 are outlined in Sections 7.2.2 and 7.2.4. Pembrolizumab will be administered at a fixed dose of 200 mg IV every 3 weeks, which will not be modified.

Participants may receive study medication for up to 36 cycles. Participants will be treated until progressive disease, unacceptable toxicity, intercurrent illness that prevents further administration of treatment, Investigator's decision to withdraw treatment, participant withdrawal of consent, pregnancy of the participant, noncompliance with study medication or procedure requirements, participant completes treatment, or administrative reasons requiring cessation of treatment, at which point they will be discontinued from the study.

All participants will be followed for at least 30 days after their last dose of MK-7162 for AE monitoring. Serious adverse events will be collected for 90 days after discontinuation, 30 days if the participant initiates new anticancer therapy less than 30 days after study treatment discontinuation, or the day new anticancer therapy is initiated if between 30 days and 90 days after study treatment discontinuation. Participants with an ongoing AE of Grade  $> 1$  at the time of treatment discontinuation will be followed until resolution of the AE to Grade 0-1, until considered stable by the treating physician, or until beginning a new anticancer therapy, whichever occurs first.

Participants who discontinue treatment for reasons other than confirmed progressive disease will have post-treatment follow-up for disease status (including imaging) until disease progression, initiating a new anticancer therapy, withdrawing consent for study participation, or becoming lost to follow-up.

After confirmed disease progression, each participant who discontinues treatment will be contacted by telephone every 12 weeks ( $\pm 14$  days) for survival until withdrawal of consent to participate in the study, becoming lost to follow-up, death, or end of the study, whichever occurs first.

Specific procedures to be performed during the trial, as well as their prescribed times and associated visit windows, are outlined in the Trial SoA - Section 2. Details of each procedure are provided in Section 9 – Study Assessments and Procedures.

This trial will use an adaptive design based on prespecified criteria. Interim analyses will be conducted to examine clinical trial data on a continuous basis to allow for dose-finding decisions, safety, tolerability, and efficacy analysis.

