Whole Blood for Immune profiling	X	X		X		X		X					Obtain during Screening Treatment Cycles: Obtain predose on C1D1, C2D1, C3D1, and C4D1	
Blood for Serum Biomarker Analysis		X		X		X		X	X	X			Treatment Cycles: Obtain predose on D1 of every Cycle.	
Blood for RNA Analysis		X		X		X		X		X			Treatment Cycles: Obtain predose C1D1, C2D1, C3D1, and C6D1 only	

Trial Phase:	Screening	Treatment (Treatment Cycle = 21 days)							End of Treatment (EoT)	Post-treatment		Notes	
		MK-7162 Mono-therapy		MK-7162 and Pembrolizumab Combination Therapy						Last Dose / Discontinuation	Safety Follow-up		
		C1		C2		C3		C4	C5 thru C36		30 days after the last dose	Every 12 weeks after the last dose	
Scheduling Day (D):		D1	D15	D1	D15	D1	D15	D1	D1				
Schedule Window (Days):	-28 to -1		± 3	± 3	± 3	± 3	± 5	± 3	± 3	± 7	± 7	± 14	
Tumor Tissue Collection													
Archival Tumor Tissue	X												Archival tumor tissue is preferred. If archival tumor tissue is unavailable, freshly obtained biopsy tissue may be used (See Procedures Manual for details).
Tumor Biopsy	X												Collection of a newly biopsied tumor tissue specimen is required during screening prior to C1D1 dosing. Must be collected after overnight fast.
Tumor Biopsy				X			X						
 
Initial requirement: C2D1 = mandatory and C3D15 = optional
 
Upon site notification by Sponsor: C2D1 = optional and C3D15 = mandatory
 
All biopsies must be collected after an overnight fast and prior to administration of either MK-7162 or pembrolizumab on the day of the biopsy.
 
 C2D1: Obtain biopsy predose C3D15: Obtain biopsy predose (after 5 additional weeks of MK-7162 in combination with pembrolizumab following C2D1).

Abbreviations: AE = adverse event; CT = computed tomography; DNA = deoxyribonucleic acid; ECG = electrocardiogram; GGT = gamma glutamyl transferase; HIV = human immunodeficiency virus; LDH = lactate dehydrogenase; MRI = magnetic resonance imaging; PET = positron emission tomography; PT/INR = prothrombin time/international normalized ratio; PTT/aPTT = partial thromboplastin time/activated partial thromboplastin time; RECIST 1.1 = Response Evaluation Criteria In Solid Tumors version 1.1; iRECIST = immune-based RECIST; RNA = ribonucleic acid; SAE = serious adverse event; T3 = total triiodothyronine; T4 = total thyroxine; TSH = thyroid stimulating hormone.

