### 5.1.2 Study Diagram

The trial design is depicted in [Figure 1](#).

Figure 1 Study Diagram

MK-7162 in Combination with Pembrolizumab				
MK-7162 @ 25 mg QD	MK-7162 @ 50 mg QD	MK-7162 @ 100 mg QD	MK-7162 @ 200 mg QD	MK-7162 @ 400 mg QD
Pembrolizumab @ 200 mg IV Q3W	Pembrolizumab @ 200 mg IV Q3W	Pembrolizumab @ 200 mg IV Q3W	Pembrolizumab @ 200 mg IV Q3W	Pembrolizumab @ 200 mg IV Q3W

- ❖ Dose escalation and confirmation using an mTPI design based on a 6 week DLT observation period to identify a preliminary RP2D
- ❖ One 3-week treatment cycle of MK-7162 monotherapy is followed by MK-7162 combination with pembrolizumab for 35 treatment cycles (total of 36 cycles on treatment)
- ❖ MK-7162 is administered orally QD. Pembrolizumab is administered by IV infusion, and is administered on Day 1 of each 3 week treatment cycle
- ❖ Treatment of the first and second participants enrolled in each cohort will occur at least 7 days apart. Treatment of the second and third participants enrolled in each cohort will occur at least 3 days apart
- ❖ Once participants have achieved the study objectives or the study has ended, they will be discontinued from this study and may be enrolled into an extension study to continue protocol-defined assessments and treatment.

IV=intravenous; mTPI=modified toxicity probability interval; QD=once daily; Q3W=every 3 weeks; RP2D=recommended Phase 2 dose

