### **9.7 Pharmacodynamics**

Venous blood samples will be collected after an overnight fast for measurement of plasma levels of KYN and TRP in participants treated with MK-7162. Sample collection, storage and shipment instructions for blood samples will be provided in the Procedures Manual.

Urine samples will be collected for measurement of MK-7162. Sample collection, storage and shipment instructions for urine samples will be provided in the Procedures Manual.

Intratumoral KYN and TRP will be measured using required as well as optional on-study tumor biopsy specimens. Unless deemed medically unsafe by the Investigator, all participants will be required to undergo a baseline biopsy during Screening, following an overnight fast. Unless deemed medically unsafe by the Investigator, participants will be required to undergo one of two additional biopsies. Initially this second biopsy will occur on Cycle 2 Day 1, after an overnight fast and prior to the initial dose of pembrolizumab. The additional optional biopsy on Cycle 3 Day 15, will also occur following an overnight fast. As the trial progresses, the Sponsor may designate the Cycle 3 Day 15 biopsy as required, with the Cycle 2 Day 1 biopsy designated as optional.

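### Does the Sponsor's undefined switch of the mandatory biopsy from Cycle 2 Day 1 to Cycle 3 Day 15 undermine the intratumoral dose-PD aims?

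*Combined protocol and SAP*

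**What the plan says.** Section 5.1.1 gives the C2D1 biopsy its purpose: "This will allow full characterization of the MK-7162 dose and intratumoral PD response relationship after three weeks of MK-7162 monotherapy". It then provides for a change: "After a sufficient number of biopsy specimens at the Cycle 2 Day 1 timepoint have been collected, the Sponsor may notify the sites" that C2D1 becomes optional and C3D15 required. The later biopsy has its own purpose. "Characterization of the MK-7162 dose and intratumoral PD response relationship at this time point will confirm whether" the effect seen on monotherapy persists; in the protocol's words, it is to "confirm whether the intratumoral PD effect of a given MK-7162 dose is maintained during concurrent PD-1 blockade with pembrolizumab".

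The Schedule of Activities (Section 2.1) repeats the switch: "Upon site notification by Sponsor: C2D1 = optional and C3D15 = mandatory". Section 9.7 has: "As the trial progresses, the Sponsor may designate the Cycle 3 Day 15 biopsy as required", with C2D1 then optional. None of the three places states how many specimens are enough, whether the count is per dose or overall, or which participants a notice binds.

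Three other provisions matter:
- Section 7.3 opens each dose level only after the previous cohort's 42-day DLT window.
- Section 5.5.3.1 allows 3 to 6 participants at a new dose.
- Section 5.1.1 lets PD data contribute to dose choice: "the preliminary RP2D may be selected based on overall exposure, emerging safety and tolerability data, PK data, PD data" and preliminary clinical benefit.

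**The concern.** Each participant owes only one on-study biopsy, and doses are filled one after another. If the switch is a single event for the whole trial, the doses enrolled before it supply C2D1 tissue and those enrolled after it supply C3D15 tissue. Time point then runs together with dose. An early switch leaves the upper doses without mandatory monotherapy tissue. A late switch leaves mandatory C3D15 tissue at the top dose only, so there is no dose relationship at that time point. In both cases the check that a dose's intratumoral effect holds under pembrolizumab is assured at about one dose, and the date of the notice decides which.

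Kynurenine and tryptophan (KYN, TRP) are the measures for secondary objective 2, Section 5.4.1.4.1 takes their ratio in tumor as well as plasma, and PD data may inform the preliminary RP2D. Tissue that was never collected cannot be recovered at analysis.

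**Working it through.** **Inputs.** Section 10.9's example without DLTs has 3 participants at each of 25, 50, 100 and 200 mg and 14 at 400 mg: 4 × 3 + 14 = 26, which reproduces the stated figure. There is one mandatory on-study biopsy per participant (Section 5.1.1). Optional biopsies are not counted, and every mandatory biopsy is taken to yield a specimen.

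**One trial-wide notice after participant k (N = 26).** r is the Pearson correlation of dose rank (1 to 5) with time point (0 or 1).

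| Notice after k | Doses with at least 3 C2D1 | Doses with any C3D15 | Doses with both time points | r |
|---|---|---|---|---|
| 3 | 1 | 4 | 0 | 0.70 |
| 8 | 2 | 3 | 1 | 0.90 |
| 9 | 3 | 2 | 0 | 0.92 |
| 12 | 4 | 1 | 0 | 0.85 |
| 15 | 5 | 1 | 1 | 0.68 |
| 19 | 5 | 1 | 1 | 0.48 |
| 23 | 5 | 1 | 1 | 0.29 |

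No k gives more than one dose with both. Extending the notice to participants already on treatment does not help. When a new cohort first reaches C2D1 (its day 22), the previous cohort's last participant is at day 43 + 21 = 64 or later, past C3D15 (day 57).

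**What limits the overlap.** A dose with 3 participants yields 3 mandatory specimens under any rule. Three per time point at all five doses needs 5 × 6 = 30 specimens, and the example has 26. On that path, the limit is one biopsy per participant, whatever the wording of the notice.

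**A fixed allocation as the alternative.** At each dose, let the first 3 participants have C2D1, the next 3 C3D15, and alternate from the seventh.
- N = 26: C2D1 3/3/3/3/7 and C3D15 0/0/0/0/7. One notice after k = 12 + 7 = 19 gives the same layout.
- N = 38 (6/6/6/6/14, an assumed layout): 3/3/3/3/7 at both time points, so five doses overlap, against at most one for a single notice at any k.

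**Precision.** The variance of a time-point contrast stratified by dose, assuming one common shift, is σ² / Σ[n₁n₂/(n₁+n₂)].
- 14-participant dose alone, 7 against 7: 49/14 = 3.5, so 1/3.5 = 0.286σ². This is also the best any single notice achieves, at N = 26 or N = 38.
- One lower dose, 3 against 3: 9/6 = 1.5, so 0.667σ².
- N = 38, all five doses pooled: 4 × 1.5 + 3.5 = 9.5, so 0.105σ².

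The fall from 0.286 to 0.105 therefore comes wholly from pooling four small lower-dose contrasts under the common-shift assumption. Compared with a notice after k = 31 (C2D1 6/6/6/6/7), it costs half the C2D1 tissue at each lower dose, 6 down to 3.

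**With de-escalation.** Table 1 dose finding was simulated, 5,000 trials for each of four assumed DLT curves over the five doses (0.02/0.04/0.06/0.08/0.10; 0.05/0.08/0.12/0.20/0.30; 0.05/0.10/0.20/0.30/0.45; 0.10/0.20/0.30/0.45/0.55). The table gives ranges across the curves. The well-timed notice is sent when a dose first reaches 9 participants.

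| | Well-timed notice | Fixed allocation |
|---|---|---|
| Mean doses with both, cohorts of 3 | 1.00–1.03 | 1.55–1.93 |
| Mean doses with both, first cohort of 6 | 1.00–1.01 | 2.97–4.91 |
| Chance of at least 3 at each time point at the most-enrolled dose, cohorts of 3 | 0.88–0.93 | 0.97–1.00 |

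**The case for a change.** The best case for a change is that silence on scope is itself the fault. Sites cannot tell whether a notice covers one dose or all. The protocol argues that IDO1 rises during immune responses, so monotherapy tissue cannot stand in for combination tissue, and plasma does not answer an intratumoral question. A per-dose rule would cost some wording and a flag in the IVRS/IWRS, with no extra mandatory biopsy. If first cohorts were six, the gain in overlap would be large.

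Much of this stands. The count, the scope and the participants bound are unstated. One trial-wide notice does limit assured overlap to about one dose, occasionally two after de-escalation. Optional biopsies and Part B may add tissue, but neither is assured.

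Three things weigh against acting on it. First, the reading that makes it a fault is not in the text. All three places describe an option for the Sponsor, and the trigger follows directly on the aim of full characterization at C2D1, which points to a late or dose-by-dose notice. The high correlations (0.70 to 0.92, k = 3 to 14) belong to notices sent before all five doses have 3 C2D1 specimens. Second, the large gain rests on six per dose, whereas Section 5.5.3.1 requires three. Third, a per-dose rule has its own trouble. Section 5.1.2 has "Treatment of the first and second participants enrolled in each cohort will occur at least 7 days apart", and Section 5.1.1 puts the third at least 3 days after the second. At that pace, with participants 4 to 6 starting up to 3 days apart, the sixth starts by day 19 (counting the first dose as day 0), before the first participant reaches C2D1 on day 21. A failed C2D1 specimen could not then be made up within that cohort. With slower accrual, making it up takes a C3D15 slot.

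**Conclusion.** No change follows. The gap is real but it is one of detail, and the people running the trial can fill it sensibly: they choose when to send the notice, the notice itself can say which doses and participants it covers, and the natural analysis compares time points within dose. A notice after 15 to 23 of 26 participants serves the C2D1 relationship at all five doses and the persistence check at the best-enrolled dose. What it does not give is a mandatory C3D15 dose relationship. On the protocol's example, three specimens per time point at every dose is out of reach under any rule with one biopsy per participant.

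More formal allocation is a debatable trade-off. It adds no overlap at N = 26. With cohorts of 3 it adds roughly half a dose to one dose on average. With six per dose it adds more, at the price of half the lower-dose C2D1 tissue. Those lower-dose comparisons of 3 against 3 would stay descriptive: if 20% or 40% of C3D15 biopsies failed (assumed), the chance of at least 2 of 3 specimens is 0.90 or 0.65.

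The stakes are small. DLT assessment is untouched, PD is one of several inputs to a preliminary dose, and plasma KYN and TRP are scheduled in both the monotherapy and combination phases at every dose. The conclusion rests on the Sponsor not sending an early trial-wide notice, which would sit badly with the stated C2D1 aim.
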